### 8.1.2 DEFINITION OF UNANTICIPATED PROBLEMS (UAP)

This study will use the COMIRB definition of UAP.

- Any event or information that was unforeseen and indicates that the research procedures caused harm (including physical, psychological, economic, or social harm) to participants or others or indicates that participants or others are at increased risk of harm than was previously known or recognized.

## 8.2 CLASSIFICATION OF AN ADVERSE EVENT

### 8.2.1 SEVERITY OF EVENT

For AEs not included in the protocol-defined grading system, the following guidelines will be used to describe severity.

- **Mild** – Events require minimal or no treatment and do not interfere with the participant's daily activities.
- **Moderate** – Events result in a low level of inconvenience or concern with the therapeutic measures. Moderate events may cause some interference with functioning.
- **Severe** – Events interrupt a participant's usual daily activity and may require systemic drug therapy or other treatment. Severe events are usually potentially life threatening or incapacitating.

### 8.2.2 EXPECTED ADVERSE EVENTS

The PI, [name] will be responsible for determining whether an AE is expected or unexpected. An AE will be considered unexpected if the nature, severity, or frequency of the event is not consistent with the risk information previously described for the study intervention.

## 8.3 TIME PERIOD AND FREQUENCY FOR EVENT ASSESSMENT AND FOLLOW-UP

The PI will record all reportable events with start dates occurring any time after informed consent is obtained until the completion of the 12-Week follow-up measures. At each study visit, the investigator will inquire about the occurrence of AE/ SAEs since the last visit. Events will be followed for outcome information until resolution or stabilization.

## 8.4 REPORTING PROCEDURES

### 8.4.1 ADVERSE EVENT REPORTING

The sponsor-investigator must record non-serious adverse events and report to DSMC and IRB according to timetable for reporting specified in the Data Safety Monitoring Plan and per COMIRB's reporting requirements. Reporting will be done by the OCRST and [name].

### 8.4.2 UNANTICIPATED PROBLEM REPORTING

This study will follow COMIRB's guidance for UAP reporting and the DSMC's requirements (discussed below). AEs, noncompliance and protocol violations will be recorded and reported as required either promptly (within 5 days of Sponsor-Investigator's knowledge) or at the time of the study's continuing review.

It is the responsibility of the OCRST and PI to report incidents or events that meet the criteria for UAPs reporting to their IRB using the IRB's standard UAP form. The OCRST and PI are responsible for reporting the UAP to the UCCC DSMC, if applicable.

## 8.5 SAFETY OVERSIGHT

The principal investigator will be responsible for the conduct of this study, overseeing participant safety, executing the data and safety monitoring (DSM) plan, and complying with all reporting requirements to local and federal authorities. This oversight will be accomplished through additional oversight from the Data and Safety Monitoring Committee (DSMC) at the University of Colorado Cancer Center (CU Cancer Center). The DSMC is responsible for ensuring data quality and study participant safety for all trials at the CU Cancer Center. A summary of the DSMC's relevant activities is as follows:

- Conduct of internal audits
- May submit recommendations for corrective actions to the CU Cancer Center's Executive Committee

Study audits conducted by the DSMC will consist of a review of the regulatory documents, consent forms, and source data verification. Documentation of the audit conducted by the DSMC will then need to be submitted to the IRB of record at the time of the IRB's continuing review of this trial (if applicable).

## 9 CLINICAL MONITORING

Clinical site monitoring will be conducted to ensure that the rights and well-being of human participants are protected, that the reported trial data are accurate, complete, and verifiable, and that the conduct of the trial is in compliance with the currently approved protocol/ amendment(s), with GCP, and with applicable regulatory requirement(s).

Monitoring for this study will be performed by CU Cancer Center Clinical Monitor in accordance with the clinical monitoring plan (CMP), incorporated herein by reference. The CMP describes in detail who will conduct the monitoring, at what frequency monitoring will be done, at what level of detail monitoring will be performed, and the distribution of the monitoring reports.

Independent audits will be conducted by the CU Cancer Center DSMC to ensure monitoring practices are performed consistently across all participating sites, if applicable, and that monitors are following the CMP.

## 10 STATISTICAL CONSIDERATIONS

### 10.1 STATISTICAL HYPOTHESES

- Primary Efficacy Endpoint(s):  
Participants will find the intervention acceptable. Implementation of intervention will be feasible.
- Secondary Efficacy Endpoint(s):

### 10.2 ANALYSIS DATASETS

An intention-to-treat analysis dataset will be used for this study. The dataset will include demographic and clinical information from each participant's medical chart, as well as self-report data provided by each participant.

### 10.3 DESCRIPTION OF STATISTICAL METHODS

#### 10.3.1 GENERAL APPROACH

This study will employ an effectiveness-implementation hybrid design (Type 1) [14], including a randomized controlled trial.

- Descriptive statistics: Categorical data will be presented as frequencies and percentages. Continuous variables will be presented using appropriate measures of central tendency.
- Inferential tests: Inferential tests will be one-tailed using an alpha level of .05.
- Covariates: We will compare treatment and control groups across all relevant demographic and medical variables to ensure randomization resulted in an equal distribution across groups. If differences are found among these variables, they will be included as covariates and subsequent models.
- For all dependent variables, we will check for normality by examining skew and kurtosis. For variables that violate normality, we will use nonparametric bootstrapping to estimate standard error and 95% confidence intervals. Additionally, we will also assess the data for violations of sphericity.

---

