- **Changes in physical and emotional functioning** in the intervention group will be compared to the control group over time. The primary outcomes are physical and emotional functioning as measured by the SF-36. We hypothesize that improvements in physical and emotional functioning will occur in both groups over time but will be greater for the intervention group at completion of the program and at six and 12-week follow-ups as compared to the TAU group.

**Aim 3: To conduct exploratory analyses on pain interference, pain intensity, and psychological flexibility (chronic pain and cancer specific), which have been identified in the literature as secondary outcomes and process outcomes of ACT in chronic pain.**

- **Changes in pain interference, pain intensity, and psychological flexibility (chronic pain and cancer specific)** will be compared over time as exploratory outcomes between the intervention group and the TAU group. We hypothesize that improvement in these variables will occur in both groups over time but will be greater in the intervention group at completion of the program and at six and 12-week follow-ups.

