## 2.3 POTENTIAL RISKS AND BENEFITS

### 2.3.1 KNOWN POTENTIAL RISKS

There are minimal risks to study participants. However, the ACT intervention, as well as measures included in assessment for all participants, will ask participants to reflect on both physical and psychological constructs that may be related to their cancer experience. This may result in distress. In the event that distress is acute, psychosocial support will be available for all participants. It is the expectation that participants in both groups will experience some benefit from active pain management intervention. All ACT groups will be directed by a licensed clinical psychologist in order to monitor for any distress in the group. Additionally, assessments of emotional functioning and pain experience (i.e., interference and severity) will be measured at the midpoint of the intervention in order to assess for any possible iatrogenic effect. These measures are precautionary in nature as there are no known potential risks for this intervention.

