### 10.3.3 ANALYSIS OF THE SECONDARY ENDPOINT(S)

Repeated measures ANOVA will be used to test the effect of the treatment on the outcomes over time. In regards to the hypotheses related to specific aim 1, outcomes including physical/emotional functioning, will be compared between treatment groups using separate repeated measures ANOVA with 5 measurement time points. Data will be presented as unstandardized beta coefficients and their respective standard errors. T-tests and chi-squares will be used to compare demographic variables between participants who complete the study and those who do not. Listwise deletion will be used when data is not missing for more than 10% of participants and there are no differences on demographic variables between completers and non-completers. If data are missing for more than 10% of participants or if there are demographic

differences between completers and non-completers, Full Information Maximum Likelihood will be used to estimate missing data.

---

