#### **10.3.5 BASELINE DESCRIPTIVE STATISTICS**

Relevant demographic constructs (i.e., age, race/ethnicity), as well as baseline assessments of primary and exploratory measures (e.g., physical and emotional functioning, pain severity and intensity, and measures of psychological flexibility), will be compared using two sample t-tests and chi-square analyses.

---

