### Aim 2:

A previous study of ACT for chronic pain management [30], using the same measures of physical and emotional functioning (e.g., the SF-36), found moderate ( $d = 0.61$ ) to large effects ( $d = 0.97$ ) at post treatment, respectively. Sample size was estimated using  $d = 0.61$ , with power at 0.80 and  $\alpha = .05$ , two-tailed. It is assumed that the correlation between pre and post-test measures will be high at .5. With these parameters and using repeated measures ANOVA to evaluate treatment difference, sample size is powered for clinical outcomes at 92 participants; with an estimated 30% attrition and conservatively including the possibility of screening failures, a maximum sample of 140 participants will be targeted for enrollment. Power was calculated using the FactorialPowerPlan Macro for SAS. See above section 10.3.2 for

missing data plan. The maximum number of participants that can be enrolled is 140, allowing for 30 % attrition and possible screening failures.

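### Section 10.3.1 tests one-tailed at .05 but section 10.4 sizes the SF-36 comparison two-tailed at .05, so a single-df contrast favouring ACT carries a 5% false-positive rate instead of the planned 2.5%

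*Combined protocol and SAP*

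**What the plan says.** Section 10.3.1 (General Approach) gives one rule for all testing: "Inferential tests will be one-tailed using an alpha level of .05". It makes no exception for any endpoint or type of test.

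Section 10.4 (Aim 2) gives the planning basis for the SF-36 outcomes: "Sample size was estimated using $d = 0.61$ , with power at 0.80 and $\alpha = .05$ , two-tailed". It also assumes a pre-post correlation of .5 and arrives at 92 participants, with a maximum enrolment of 140.

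Section 10.3.3 says that physical and emotional functioning "will be compared between treatment groups using separate repeated measures ANOVA with 5 measurement time points", with results shown as unstandardised betas and standard errors. It does not restate the sidedness, so 10.3.1 governs. Section 10.3.10 is the same for the exploratory outcomes. Under section 10.3.5, baseline variables "will be compared using two sample t-tests and chi-square analyses".

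Section 2.2 (Aim 2) states the direction expected: improvement in both groups, "but will be greater for the intervention group at completion of the program and at six and 12-week follow-ups".

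**The concern.** The sample size and the analysis of the same comparison use different significance criteria. Total nominal alpha is .05 in both places. What differs is the share lying in the direction of benefit: .05 under 10.3.1 and .025 under 10.4. An SF-36 contrast with a one-sided p-value between .025 and .05 is therefore significant under one section and not under the other.

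Three things follow.

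- **Choice after the fact.** Section 10.5.1 says there is no blinding, and section 10.3.6 has the investigators monitoring data throughout. If the conflict stays, the criterion could be chosen once results by arm are known.
- **Worsening cannot be declared.** A test directed toward benefit can never call a worsening under ACT significant. Yet section 2.3.1 allows for that possibility: emotional functioning and pain "will be measured at the midpoint of the intervention in order to assess for any possible iatrogenic effect".
- **The rule does not fit the named tests.** The group-by-time F test over five time points and the chi-square tests are non-directional. The baseline and completer t-tests have no hypothesised direction, yet they select covariates (10.3.1) and the missing-data method (10.3.3).

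**Working it through.** **Inputs.** From section 10.4, Aim 2: d = 0.61, power 0.80, alpha .05 two-tailed, pre-post correlation r = .5, N = 92. From 10.3.1: alpha .05 one-tailed. From 10.5.1: 1:1 allocation, hence 46 per arm. From the synopsis and 10.4, Aim 1: minimum enrolment 50, hence 25 per arm.

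**Approximation.** The plan names a repeated measures ANOVA but no single-df contrast. I use a two-sample t-test on change from baseline. With r = .5 the change score has variance 2(1 − .5) = 1 in units of the raw variance, so d is the same on either scale.

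**1. The plan's own figure.** Normal formula, two-tailed: n per arm = 2(1.960 + 0.842)²/0.61² = 42.2, so 43, total 86. The noncentral t gives 44 per arm, total 88. One-tailed: 2(1.645 + 0.842)²/0.61² = 33.2, so 34, total 68. None of these equals 92; the closest is 88, two-tailed. The plan used a SAS macro whose full settings are not given, so this does not show that 92 is wrong. It does show that 92 fits the two-tailed basis much better than the one-tailed one. The conflict does not depend on how 92 was obtained.

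**2. False-positive rate in favour of ACT.** One-tailed .05 puts .05 in that tail. Two-tailed .05 puts .05/2 = .025 there. This needs no approximation.

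**3. Significance threshold and power.** The smallest significant observed d is t_crit × √(2/n). Power is from the noncentral t, with noncentrality 0.61 × √(n/2).

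| | One-tailed .05 | Two-tailed .05 |
|---|---|---|
| 46 per arm (df 90): critical t | 1.662 | 1.987 |
| smallest significant d, t × √(2/46) | 0.347 | 0.414 |
| power at d = 0.61 | 0.896 | 0.825 |
| 25 per arm (df 48): critical t | 1.677 | 2.011 |
| smallest significant d, t × √(2/25) | 0.474 | 0.569 |
| power at d = 0.61 | 0.685 | 0.561 |

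**4. A worsening.** Suppose, for illustration only, a true d of −0.61 with 46 per arm. By symmetry a two-tailed test declares it with probability 0.825. The test toward benefit has rejection probability below 0.00001, and any such rejection would be in the wrong direction.

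**5. The omnibus test.** Group by time over five time points has 4 numerator df. With N = 92, complete data and sphericity, error df = 4 × 90 = 360. F(4,360) at upper-tail .05 is 2.40. The F statistic does not carry the sign of the differences, so a one-tailed instruction cannot be carried out on it.

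**The case against.** The strongest reply is that the conflict barely touches the analysis the plan names. At the ordinary upper-tail .05, the group-by-time F test has the same critical value, 2.40, under either section. The betas in 10.3.3 are to be presented, not explicitly tested, and section 2.2 states hypotheses at three times without naming a contrast. This stands as a limit on the effect: the 5% against 2.5% applies to single-df contrasts only. It does not remove the conflict, because a hypothesis of greater improvement at stated times can be answered only by such contrasts. A reading of the one-tailed rule as allowing .10 in the upper tail of F (critical value 1.96) has no support in the text, and I give it no weight.

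The second reply is that a prespecified direction is the usual ground for one-tailed testing, and sections 2.2 and 4.2.2 give one. That is a possible justification, but the document never offers it as one, and the same comparison was sized two-tailed.

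Third, harm is watched by other means. The midpoint scores can be read descriptively, and section 8.3 provides that "At each study visit, the investigator will inquire about the occurrence of AE/ SAEs since the last visit". This is correct, and it weakens the argument from harm. A true worsening of 0.61 is only the planning effect with its sign reversed.

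Fourth, two-sided testing costs power if enrolment stops near the minimum: 0.561 against 0.685 at 25 per arm. If 50 enrol and 30% are lost (17 to 18 per arm), power is about 0.41 to 0.43 against 0.54 to 0.56. This is a real cost, but low power at the minimum is a matter for the enrolment range and does not justify a looser criterion than the one used to size the trial.

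**Conclusion.** The concern holds. Sections 10.3.1 and 10.4 contradict each other on sidedness, and the one-tailed rule cannot be applied to the F and chi-square tests. For a single-df contrast, the false-positive rate in favour of ACT is twice the planned one. At 46 per arm the threshold falls from an observed d of 0.41 to 0.35.

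The two error rates follow from the text alone. The thresholds and powers rest on a two-sample t approximation to change from baseline at r = .5, not on the planned ANOVA. The consequence is moderate. It is confined to the secondary SF-36 outcomes and the exploratory outcomes, and to results with a one-sided p between .025 and .05. Feasibility, acceptability and fidelity are untouched. It should be fixed.

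**What to change.** Replace the sentence in 10.3.1 with: *Treatment contrasts will be tested two-sided at alpha .05, with two-sided 95% confidence intervals. Omnibus F and chi-square tests are non-directional at alpha .05. Baseline and completer comparisons are two-sided.* This matches 10.4 and, if the bootstrap intervals already planned in 10.3.1 are the usual two-sided kind, those as well.

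Name the contrasts in 10.3.3, for example ACT versus TAU at week 8 and at the 6- and 12-week follow-ups, as hypothesised in section 2.2. Three times on two subscales makes six tests, which section 10.3.8 does not address; that is a separate question.

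Date the change and state that it was made before any outcome analysis by arm. This matters because the study is unblinded and section 5.3 dates the in-person phase from January 2019.

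The cost is a short text change and one amendment for board approval (section 13.2). No participants need to be added: 86 to 88 suffice under the approximation above, the plan has 92, and 92/0.7 = 131.4, so 132, fits under the maximum of 140. The price is a stricter criterion, which the sample size already assumes, and the lower power near the 50-participant minimum, which the amendment should report.

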*Medical information.* Relevant medical information will be collected both from the patient at the pre-intervention assessments as well as from chart review of the University of Colorado Hospital electronic health record (EHR). When patient report and EHR are in conflict, EHR data will be preferred. Relevant medical information includes medications pertaining to pain management (e.g., opioid and non-opioid analgesics), medical pain management services (e.g., nerve blocks, spinal cord stimulator), behavioral pain management services (e.g., massage, acupuncture, physical therapy), and medications pertaining to psychiatric symptoms (given their impact on the primary outcome). Other relevant medical information will include data directly related to the patient's cancer treatment, including diagnosis, as well as type and duration of treatment.

*Physical/Emotional Functioning.* The Medical Outcomes Study 36-item short-form health survey (SF-36) is a self-report measure of health related quality of life that includes subscales for both physical functioning and emotional well-being [17]. The physical functioning subscale includes 10 items evaluating the occurrence and severity of physical difficulties, with a higher subscale score indicating better levels of physical functioning. The subscale specifically asks, “Does your health now limit you in these activities? If so, how much?”, and then provides a number of activities related to daily living (e.g., climbing stairs, bathing or dressing) as well as exercise behaviors (e.g., walking more than one mile, vigorous activities such as strenuous sports). Item responses are made on a 3-point Likert scale with one indicating “Yes, limited a lot,” two indicating “Yes, limited a little,” and three indicating “No, not limited at all.” This subscale has excellent internal consistency with a Cronbach’s alpha of .93 [18].

The emotional well-being subscale of the SF-36 includes five items evaluating how patients have felt during a previously identified period, with a higher subscale score indicating higher levels of positive affect. Specifically, items ask questions such as “Have you been a very nervous person?” and “Have you felt calm and peaceful?” Item responses are made on a six point Likert scale with one indicating “All of the time” and six indicating “none of the time.” This subscale has excellent internal consistency with a Cronbach’s alpha of .90 [18].

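### Section 10.3.1 picks covariates for the efficacy models by chance baseline imbalance instead of prognostic value, so the reported model depends on the data; any power cost depends on which contrast is tested

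*Combined protocol and SAP*

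**What the plan says.** Section 10.3.1 is the only place that deals with covariates. It begins "We will compare treatment and control groups across all relevant demographic and medical variables" and continues "If differences are found among these variables, they will be included as covariates and subsequent models". It gives no list of variables and no definition of a difference. Section 10.3.5 says that demographic variables and the baseline outcome scores "will be compared using two sample t-tests and chi-square analyses". It sets no significance level for those tests.

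The efficacy analyses in sections 10.3.3 and 10.3.10 name no covariate, and section 10.5.1 names no stratification factor. The model for the SF-36 outcomes is "separate repeated measures ANOVA with 5 measurement time points", with baseline as one of the five responses.

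Section 7.1 explains that the trial collects "medications pertaining to psychiatric symptoms (given their impact on the primary outcome"). Sections 2.2 (Aim 2) and 4.2.2 call SF-36 physical and emotional functioning the primary outcomes, although they are formally secondary endpoints. I read the remark in 7.1 as referring to them.

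**The concern.** For variables fixed before randomisation, any difference between the arms is chance. A baseline test therefore says nothing about whether a variable is worth adjusting for; that depends on how strongly it predicts the outcome. The rule passes over a variable that the protocol itself calls influential unless it happens to be imbalanced, and admits a variable of no prognostic value that happens to be imbalanced.

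The adjusted model is unknown until the arms have been compared. Because neither the pool of variables nor the threshold is stated, two analysts could report different treatment estimates from the same data, and sections 4.1 and 10.5.1 confirm that nobody is blinded. Precision that the collected data could supply may also be lost, but only under conditions set out in the working.

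**Working it through.** **Inputs from the protocol (section 10.4, Aim 2).** d = 0.61, pre-post correlation r = .5, two-sided alpha .05, power .80, n = 92. The minimum enrolment is 50 (synopsis).

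**Assumptions, not in the protocol.** A .05 screen for a baseline difference; independent candidate variables; covariates that explain R² = 10%, 20% or 30% of the outcome variance.

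**The plan's own figure.** n per arm = 2(1.96 + 0.84)² / 0.61², which rounds up to 43, or 86 in total; the exact t calculation gives 88. With r = .5 the change-score variance factor is 2(1 − .5) = 1, so the same figures apply to a pre-post change contrast. The stated 92 is not reproduced exactly, but it is slightly conservative: power at 92 is .825. Nothing below depends on the difference.

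**How often the rule selects by chance.** A given prognostic variable enters with probability .05 and is left out with probability 1 − .05 = .95. Sections 7.1 and 10.3.5 name 17 variables: 6 demographic (age, sex, race, ethnicity, education, marital status), 8 treatment (opioids, non-opioid analgesics, nerve blocks, stimulator, massage, acupuncture, physical therapy, psychiatric medication) and 3 cancer (diagnosis, treatment type, treatment duration). Expected chance entries: 17 × .05 = 0.85. Chance of at least one: 1 − .95^17 = .58. For 5, 10 or 20 variables it is .23, .40 or .64.

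**Power, between-group comparison of post scores.** Simulation, 8,000 trials per cell, d = 0.61, two-sided .05, 3 of 17 variables prognostic:

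| n | R² | Plan's rule | Three covariates fixed | Gap (points) |
|---|---|---|---|---|
| 92 | .10 / .20 / .30 | .81 / .82 / .82 | .85 / .89 / .93 | 4 / 7 / 11 |
| 50 | .10 / .20 / .30 | .52 / .52 / .51 | .57 / .63 / .67 | 5 / 11 / 16 |

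At R² of 20–30%, no adjustment gives .83 at n = 92 and .55–.56 at n = 50, so the rule is no better than ignoring covariates.

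**Power, change contrast, one covariate that predicts change** (40,000 trials per setting). At n = 92 the rule gives .828 / .832 / .838, against .858 / .896 / .931 when the covariate is always included: gaps of 3.0, 6.4 and 9.3 points.

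**Power, change contrast, covariate effect the same at both visits** (6,000 trials per cell, 3 of 17 prognostic). A constant effect cancels from the change.

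| n | R² | Plan's rule | Three fixed | No adjustment |
|---|---|---|---|---|
| 92 | .10 / .20 / .30 | .802 / .805 / .798 | .813 / .809 / .802 | .826 / .824 / .815 |
| 50 | .10 / .20 / .30 | .532 / .521 / .512 | .535 / .533 / .524 | .564 / .562 / .549 |

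Fixing the covariates gains about 0 to 1 point over the rule, and loses about 1 to 3 points against no adjustment.

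**Type I error under the rule.** About .045 in the first set-up and .042 to .050 in the single-covariate set-up, against a nominal .05.

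**The case against.** The strongest reply is that the power loss belongs to a model the plan does not use. Section 10.3.3 tests the treatment effect over time with baseline among the responses, and section 2.2 hypothesises greater improvement. That points to a group-by-time contrast, from which a covariate with a constant effect cancels. This stands. A reader might infer that the rule generally loses power, or discards most of the precision available; the documents do not support that. They do not settle the matter the other way either: section 10.3.3 also speaks of comparing outcomes between treatment groups and never names the contrast, and nothing in the protocol says covariate effects are constant over visits.

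A reader might also infer that choosing covariates from the data inflates false positives. It does not here; the rule is slightly conservative.

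It is also fair that no R² and no screening level appear in the protocol, that most of the 17 variables come from lists of examples and some will be correlated, and that section 10.3.1 says "Inferential tests will be one-tailed using an alpha level of .05" whereas these calculations are two-sided, as in section 10.4. One-sided, the post-score gap remains (n = 92, R² = .20: .89 against .94).

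Finally, efficacy is a secondary and preliminary aim. The rule does not touch feasibility, acceptability or fidelity. That limits the importance of the point without removing it.

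**Conclusion.** The concern holds as one of covariate selection and prespecification. The plan states a rule that selects on the wrong criterion, no other section overrides it, and it sits badly with the plan's own remark on psychiatric medication. The main consequence is a model, and so an estimate, that depends on chance imbalances judged by an unblinded analyst. This would stand even if the power cost were nil.

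The 95% omission figure rests on the assumed .05 screen; the 58% also needs independence and the illustrative count of 17. The power cost is conditional. At n = 92 it is roughly 4 to 10 points (individual settings run from 3 to 11) for post-score comparisons or covariates that predict change, and about 0 to 1 point for a pure group-by-time contrast with constant covariate effects. All of these rest on the assumed R² of 10–30%. The change is worth making, but the point is moderate: it affects secondary and exploratory results only and does not raise the false-positive rate.

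**What to change.** Delete the test-then-adjust sentence in section 10.3.1. In its place, name a short list of covariates chosen on prognostic grounds, and include it in every SF-36, PROMIS, CPAQ and CAAQ model whatever the balance. Psychiatric medication at baseline is the one candidate that the protocol itself supports; the study team should choose any others.

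Use only values that refer to the time before randomisation. This needs saying because section 7.3 records medication throughout participation and section 7.2.2 places the baseline questionnaires after randomisation. Name the contrast tested in section 10.3.3, and say whether each covariate enters with its interaction with time, since that decides whether adjustment can sharpen a group-by-time test.

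Fix the list before comparative outcome data are analysed, and state whether any have already been seen. It may be too late to claim that none have: this version is dated 03/30/2021, section 5.3 dates the in-person phase from 1/1/2019, and section 10.3.6 has investigators monitoring data throughout.

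Keep the section 10.3.5 table as description only, with no role in model choice.

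The cost is a change of wording and no new data. The downside is a few degrees of freedom, which can cost about 1 to 3 points of power if the chosen covariates do not predict the analysed contrast. That is a reason to keep the list short.
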